8.2. Research Related Procedures

	Baseline (within 28 days of Cycle 1, D1)	C1D1	C1 D15	C2 D1	C2 D15	Every 8 weeks (± 1 week) up to week 24	Cycles 4 and 6, D15
PKs per section 9.1		x ¹	x ¹				
ECG (QT study) done during PK blood collection per section 9.3. PK patients only. ²		x ²	x ²				
Serum IGF-1 level. All subjects.		x ³		x ³	x ³		
Plasma and whole blood IGF-1R level. All subjects.		x ³		x ³	x ³		x ³
Anti-765IGF antibody assay. All subjects.		x ³		x ³	x ³		x ³
Neutralizing antibodies. All subjects.		x ³		x ³	x ³		x ³
IGF-1R expression in bone marrow biopsy and aspirate by IHC and flow cytometry. All subjects.	x ⁴					x ⁴	
IGF-1R expression in blood cells by flow cytometry. All subjects.	x ⁵					x ⁵	

¹ Done only in the PK patients in the MTD. Pre-765IGF-MTX infusion (at the time of am labs if am labs are within one hour of 765IGF-MTX infusion), 5 min before the infusion ends (+/- 5 minutes), and at the following time points after completion of the infusion: 30 min (+/- 5 minutes), 60 min (+/- 15 minutes), 2 h (+/- 15 minutes), 4 h (+/- 15 minutes), 6 h (+/- 15 minutes), 8 h (+/- 15 minutes and 24 h (+/- 2 hours)). The 8 hour time point will be collected on day 1 but not on day 15.

² Done only in PK patients in the MTD. Pre-765IGF-MTX infusion (+/- 5 minutes), and 30 min (+/- 5 minutes) after starting the infusion, at the following time points after completion of the infusion: 60 min (+/- 15 minutes) and 3 hours (+/- 15 minutes). In all patients, ECG is done at baseline, on day 1, cycle 1 (before the infusion), and 30 days (± 1 week) after the final dose (see section 8.1).

³ Blood draw prior to infusion

⁴ Bone marrow biopsy and aspirate will be collected at baseline and every 8 weeks (± 1 week) up to week 24, i.e., after cycles 2, 4, and 6, before the first dose of the next cycle. If no bone marrow aspirate viably frozen for flow cytometry is available from a patient in the 28-day baseline period before cycle 1, day 1, the patient may still enroll and no new bone marrow biopsy will be required for a baseline sample.

⁵ Whole blood collection in EDTA tubes.

9. Correlative Studies

Information on the collection of blood samples for the correlative studies (collection tubes to be used, volume of blood drawn, collection processing, aliquot procedure and storage, and particular assay to be used) can be found in a laboratory manual to be supplied.

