[name]
 Mayo Clinic
 Division of Hematology
 Dept. of Internal Medicine
 [name]
 [name]
 [contact]
 [contact]
 [contact]

IND Sponsor Contact Information:

[name].,
 IGF Oncology,
 [name],
 [name]
 [contact]
 [contact]

Synopsis

Primary Objective:

The primary objective of this study is to determine the safety and tolerability of utilizing the insulin-like growth factor-1-methotrexate conjugate, 765IGF-MTX for the treatment of advanced, previously treated myelodysplastic syndrome (MDS), chronic myelomonocytic leukemia (CMML) and oligoblastic acute myelogenous leukemia (oligoblastic AML or O-AML), including determining the maximum tolerated dose (MTD).

Secondary Objective:

The secondary objective of this study is to determine the clinical benefit of 765IGF-MTX as measured by partial and complete remission rates, relapse-free survival, and overall survival in patients with advanced, previously treated MDS, CMML, or O-AML.

Patient Population:

[figure not shown]
- Diagnosis of MDS, CMML or O-AML that is refractory to or intolerant of standard therapy and is no longer likely to respond to such therapy
- Patient must have recovered from the acute toxic effects (\leq grade 1 CTCAE v.4.0) of previous anti-cancer treatment prior to study enrollment
- Age 18 years or older
- ECOG performance status 0, 1, or 2 (appendix III)

Study Design:

This pilot study will evaluate use of IGF-Methotrexate conjugate (765IGF-MTX) in patients with advanced, previously treated MDS, CMML and O-AML. 765IGF-MTX at a dose of 0.20 to 2.5 μ equivalents per kg is administered as an IV infusion over 1.5 hours on days 1, 8 and 15 of a 28 day cycle. Treatment continues until disease progression, as assessed after 2 cycles, unacceptable toxicity, or patient refusal. Assessment of response will be confirmed by bone marrow studies performed at the end of cycles 2, 4, and 6 (each +/- 3 days).

Once a final maximum tolerated dose level (MTD) is determined, the pharmacokinetics (PK) of 765IGF-MTX will be assessed on days 1 and 2 and days 15 and 16 of cycle 1 at the MTD in three patients.

Study Schema

Pharmacodynamic samples on day 1 of cycle 1, days 1 and 15 of cycle 2, and day 15 of cycles 4 and 6 before 765IGF-MTX administration.

At the MTD: Pharmacokinetic samples starting on day 1 (including time points on day 2), and day 15 (including time points on day 16) of cycle 1

Dose Finding Component: 1 cycle = 28 days

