7.1. Study Drug Administration

After Cycle #1 a new treatment cycle will be initiated when all of the following conditions are met:

- Non-hematologic treatment related toxicities have improved to grade 1 or resolved (CTCAE v.4.0)
- Platelets $> 10 \times 10^9/L$

Refer to section 7.3 for guidelines for dose modifications based on treatment-related delays and toxicities of the previous cycle.

7.1.1. 765IGF-Methotrexate Administration

765IGF-MTX will be given at the assigned dose as a 1.5 hour IV infusion in 250 ml of 5% dextrose on days 1, 8, and 15 of a four-week treatment cycle. Every 4 week period will be considered one treatment cycle. Subsequent cycles must meet the criteria found in section 7.3.1 and may begin 1 day earlier to accommodate scheduling issues, or up to 4 weeks later if a patient needs this time to recover to meet criteria for start of a new cycle as specified in section 7.2.1. At the investigator's discretion, the study drug may be administered in 10% dextrose rather than 5% dextrose if it is believed necessary to prevent or control hypoglycemia.

Pre-medication

None is required, but can be utilized per clinician discretion. The program of predication below has been used in the prior solid tumor phase I with some of the later enrolled patients to prevent nausea and an allergic reaction. Nausea during infusion was seen in a few patients and a possible allergic reaction to the drug was seen in one patient.

Zofran 8mg PO
Benadryl 50mg PO
Tylenol 650mg PO
Hydrocortisone 100mg IV push
D5 .45 normal saline 100cc/hr to start with premeds

Monitoring

Vital signs including blood pressure, pulse, temperature, respirations, and pulse oximetry, and blood glucose will be measured immediately before the infusion and immediately after completion of the infusion in all patients during all cycles. IGF-MTX causes hypoglycemia at higher dose levels, so it is important to monitor blood glucose levels. During the first 28-day cycle, patients will be monitored for blood glucose on infusion days for a total of 3.5 hours. Vital signs listed above will be monitored per the following table:

Monitoring interval	
Immediately before infusion	All vitals
To Hour 1.5 (during infusion)	Glucose only, every 15 min
Hour 1.5	All vitals
Hours 1.5-3.5	Glucose only, every 30 min

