9.5. Plasma and whole blood IGF-1R Level and 765IGF-MTX Toxicity/Response

Plasma and whole blood samples from before the infusion on D1 of cycle 1, and before the infusion on D1 and D15 of cycle 2 and on D15 of cycles 4 and 6 will be collected from each patient to determine if pre- and within-treatment serum and blood IGF-1R level is associated with 765IGF-MTX toxicity and/or response. Quantification of IGF-1R in plasma will be performed by IGF Oncology using western blotting. A descriptive analysis will be done between clinical response and marker levels. Please see the laboratory manual for biomarker collection procedures.

9.6. Formation of anti-765IGF-MTX antibodies.

Serum samples from before the infusion on D1 of cycle 1, and before the infusion on D1 and D15 of cycle 2 will be collected from each patient and analyzed for anti-drug antibodies by an assay the sponsor has used for detecting anti-765IGF-MTX antibodies in preclinical tests in dogs and rats. The assay is a sandwich ELISA involving plating serum in 96-well plates, adding drug to the wells of the plates to bind to any anti-drug antibodies that may be present in the serum, and then detecting bound 765IGF-MTX drug with an anti-IGF-HRP conjugate antibody from R&D Systems, Quantikine human IGF-1 ELISA kit.

That sandwich assay detects antibodies against 765IGF-MTX.

The serum samples will also be analyzed for the presence of neutralizing antibodies. In this assay, serum will be mixed with 765IGF-MTX in an in vitro assay for killing of human MCF7 breast cancer cells to determine whether the addition of patient serum affects the minimum inhibitory concentration of 765IGF-MTX in inhibiting growth of MCF7 cells. This assay will be performed on the same serum samples collected before treatment on Cycle 2, days 1 and 15 and on day 15 of cycles 4 and 6. Please see the laboratory manual for biomarker collection procedures.

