13.2. Statistical Methods

Statistical analyses will be performed using SAS software version 9.4 or higher. In general, data summaries will be compiled by 765IGF-MTX dose level and overall and will include the mean,

standard deviation, median, minimum and maximum values for continuous data; the median, 25th and 75th percentiles, minimum and maximum values for time-to-event endpoints; and the number and percentage of patients in each category for categorical data. Pointwise 95% confidence intervals (CI) will also be estimated for the mean (continuous data), median (time-to-event endpoints) or percentage of patients (categorical data).

Baseline value of a characteristic is defined as the last measured value prior to the first dose of 765IGF-MTX.

Descriptive statistics such as Spearman or Pearson correlation coefficients will be estimated with 95% CIs to assess the relationship between anti-765IGF antibody and anti-765IGF-MTX antibody levels with clinical response and toxicity.

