13.5.6 Antibody formation against 765IGF-MTX: Serum samples from before infusion on D1 of cycle 1, and before infusion on D1 and D15 of cycle 2 and day 15 of cycles 4 and 6 will be collected and analyzed for anti-765IGF-MTX antibodies. A descriptive analysis will be done correlating anti-765IGF-MTX antibody presence or levels with clinical response and toxicity.

13.5.7 Neutralizing antibodies and 765IGF-MTX toxicity/response: Serum samples from before infusion on D1 of cycle 1 and before infusion on D1 and D15 of cycle 2 and D15 of cycles 4 and 6 will be collected for presence of neutralizing antibodies. A descriptive analysis will be done correlating presence or levels of neutralizing antibodies with clinical response and toxicity.

13.5.8 IGF-1R expression level in bone marrow biopsies via IHC and flow cytometry and IGF-1R expression level in blood cells by flow cytometry: IGF-1R expression at baseline will be performed on paraffin-embedded fixed bone marrow aspirates by Quest Diagnostics by IHC and IGF-1R expression at baseline will be performed on fresh viable bone marrow aspirates and fresh whole blood by Charles River, Inc. by flow cytometry. If sample sizes are small and heterogeneous, clinical responses will be reported by dose and disease (MDS, CMML, or O-AML) type

14 Conduct of the Study

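### The only scheduled antibody and IGF-1R level draws after cycle 2 in section 8.2 sit on day 15 visits that the schema makes optional, so late immunogenicity may be seen only in patients whose physician keeps that visit

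*Combined protocol and SAP*

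**What the plan says.** The table in section 8.2 has a column for day 15 of cycles 4 and 6. Three rows are marked there: plasma and whole-blood IGF-1R level, the binding-antibody assay ("Anti-765IGF antibody assay. All subjects") and neutralizing antibodies. All carry footnote 3, "Blood draw prior to infusion". Serum IGF-1 is not marked in that column.

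The same late timing appears in the Study Schema text in the synopsis ("day 15 of cycles 4 and 6 before 765IGF-MTX administration"), in 9.2, in 9.5 for IGF-1R ("the infusion on D1 and D15 of cycle 2 and on D15 of cycles 4 and 6 will be collected from each" patient), in 9.7 and 13.5.7 for neutralizing antibodies, and in 13.5.6 for binding antibodies ("before infusion on D1 and D15 of cycle 2 and day 15 of cycles 4 and 6").

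Other places do not agree:

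- **Study Schema, footnote 1:** day 8 and day 15 are left to the physician from cycle 3. The marker is on the drug row as well as the clinic-visit row.
- **Section 7.1.1:** the drug is given "on days 1, 8, and 15 of a four-week treatment cycle", with no such discretion. The table in 8.1 likewise shows day 15 under each treatment cycle.
- **Section 9.6, binding antibody:** after the cycle 1 sample, only samples "before the infusion on D1 and D15 of cycle 2 will be collected from each patient and analyzed for anti-drug antibodies" are listed. Cycles 4 and 6 are absent.
- **Section 4, MTD cohort:** one sentence adds a pharmacodynamic sample in the fourth week of every cycle. The closing paragraph of the same section gives the day 15 schedule without it.

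For analysis, 13.5.6 and 13.5.7 plan to relate antibody presence or level descriptively to response and toxicity. Section 13.2 summarizes categorical data by "the number and percentage of patients in each category for categorical data". It does not say who is counted.

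**The concern.** A draw defined as pre-infusion on a given day needs a visit on that day. If the physician drops day 15 of cycle 4 or 6, as the schema allows, there is no infusion to precede and no stated alternative day. The 30-day final visit has no antibody draw in 8.2 either.

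Section 9.6 says antibodies could weaken the drug's effect and raise the risk of an anaphylactic reaction, so antibody status after longer exposure is worth knowing. The decision to keep or drop a day 15 visit may plausibly depend on how the patient is responding and tolerating treatment. Those are the two variables with which antibody status is to be correlated. A sample chosen in that way can distort the correlation whatever denominator is used.

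**Working it through.** The plan states no rate, precision or sample size for the antibody analysis, so there is no figure to reproduce. The check compares the schedules and counts draws and doses.

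**1. Draws at risk (8.2).** Post-baseline antibody and IGF-1R level draws fall on C2D1, C2D15, C4D15 and C6D15, 4 in all. Those on optional visits are C4D15 and C6D15: 2 of 4, and 2 of 2 after cycle 2.

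**2. Exposure that may go unobserved.** Count the doses given before each draw, with three doses in each of cycles 1 and 2:

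| Draw | All day 8 and 15 doses given | Only day 1 given from cycle 3 |
|---|---|---|
| C2D15 | 3 + 2 = 5 | 5 |
| C4D15 | 3×3 + 2 = 11 | 6 + 1 + 1 = 8 |
| C6D15 | 5×3 + 2 = 17 | 6 + 3 + 1 = 10 |

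The last sample not tied to an optional visit follows 5 doses. The late samples would follow 8 to 17. The right-hand column is hypothetical for sampling: on the literal schedule, a patient who skips day 15 has no draw.

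**3. What fewer samples do to precision (illustration).** Assume 9 patients still on drug at the late draw. Nine is the planned MTD cohort size; the documents do not say how many reach cycle 4. With no positives among n sampled, the exact (Clopper-Pearson) 95% upper limit is 1 − 0.025^(1/n):

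- n = 9: 33.6%
- n = 6: 45.9%
- n = 3: 70.8%

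**4. What the undefined denominator could do (illustration).** If unsampled patients were counted as negative, the apparent late rate would be the rate in sampled patients times the share sampled. Assume one third of sampled patients are positive:

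| Sampled / on treatment | Positive | Rate among sampled (95% CI) | Rate over all 9 (95% CI) |
|---|---|---|---|
| 6 / 9 | 2 | 33.3% (4.3–77.7%) | 22.2% (2.8–60.0%) |
| 3 / 9 | 1 | 33.3% (0.8–90.6%) | 11.1% (0.3–48.2%) |

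Step 4 applies only if the analysis counts patients that way. Steps 1 to 3 do not depend on it.

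**The case against.** **A workable reading exists.** Section 8.2 says all subjects, 9.5 says each patient, and 7.1.1 and 8.1 show day 15 in every cycle. A site could treat the research schedule as governing and hold the visit. That is possible, but the schema says otherwise and no section ranks the two, so sites can differ.

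**Late samples may exist elsewhere.** Section 13.5.2 lists antibodies among the pharmacodynamic parameters, so the fourth-week sample in section 4 could be read as a late antibody sample. It is mentioned for the MTD cohort only, is missing from the closing paragraph of that section, and appears in neither 8.2 nor 9.2. It is a further inconsistency, not a dependable backup. The 8-weekly blood-cell flow cytometry measures IGF-1R expression on cells and does not replace the antibody or IGF-1R level samples.

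**A reader might infer that the antibody rate will be biased low.** The documents do not support that. Section 13.2 defines no denominator. Section 13.2.1 says missing values are in general not imputed, and its one exception, a missing marrow counted as no response, concerns efficacy. Nothing puts unsampled patients in the antibody denominator, and nothing keeps them out. Section 13 also calls itself an overview and defers detail to a full SAP. No visit-specific late rate is named.

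**A reader might infer that antibodies cannot be detected at all in these patients.** They can, at C2D1 and C2D15. Only later seroconversion is missed.

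**A reader might want a percentage for what is missed.** With skip probability q per visit, an antibody detectable only at cycle 6 is missed with probability q. One detectable at both late draws is missed with probability q² if skips are independent. For an assumed q of 0.2 to 0.5 that is 20–50% and 4–25%. No q is given in the documents, and skips within a patient are unlikely to be independent. These figures are not the error in the overall antibody rate, which includes early positives.

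What stands: the bias, its direction and its size are not established. The scheduling conflict is.

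**Conclusion.** The point holds as a schedule conflict with an analytic consequence. Both late antibody and IGF-1R level draws in 8.2 can be lost in patients still on treatment, because they are attached to a visit and a dose that the schema makes optional. Late antibody formation would then be described in a subset chosen by the physician. That the choice follows response or tolerability is plausible but not stated anywhere.

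The effect cannot be sized from the documents: they give neither the number of patients reaching cycles 4 and 6 nor the frequency of skipped day 15 visits. The endpoint is correlative and descriptive, and cycle 2 samples are unaffected, so the point is minor. It is still worth correcting before enrolment, because a later SAP can define a denominator but cannot recover a sample that was never drawn.

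**What to change.** **Sampling.** Either take these draws before the dose on day 1 of cycles 4 and 6, or state that the cycle 4 and cycle 6 sample is required whether or not a day 15 infusion is given. The first option keeps the number of draws and uses a visit that footnote 1 does not make optional. Its cost is a sample about 2 weeks earlier, after 9 and 15 doses rather than 11 and 17 if every dose is given. The second keeps the timing but may need a visit for the blood draw alone.

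Do not move the draws to day 1 of cycles 5 and 7 alone. Those days follow the marrow assessments at the end of cycles 4 and 6. Patients who stop because of that assessment would not be sampled, which would tie sampling directly to response.

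**Analysis.** In 13.5.6 and 13.5.7, define the denominator as patients with an evaluable sample in the period, and report the number on treatment but not sampled. This prevents dilution and makes the gap visible. It does not remove selection, which is why the sampling change comes first.

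**Reconciliation.** Bring the Study Schema and sections 4, 7.1.1, 8.1, 8.2, 9.6 and 13.5.6 into agreement on the status of day 15 from cycle 3 and on the sampling days, including the fourth-week sample and the cycle 4 and 6 binding-antibody draws. If the draws move to day 1, also update 9.2, 9.5, 9.7 and 13.5.7. Which dosing or visit rule is right is for the sponsor and investigators; this point takes no position on it.

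The total cost is a schedule-table edit, matching text edits and one or two sentences in the analysis plan.

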9.1. Pharmacokinetics

9.1.1. Pharmacokinetic Sample Collection

The pharmacokinetics of 765IGF-MTX will be examined following the doses administered on days 1 and 15 of cycle 1. On these days the 765IGF-Methotrexate will be infused in the morning as described in section 7.1.1. The research team will record the start and stop times of the infusion and volume of the 765IGF-MTX solution infused. Whole blood (6 mL) will be collected from an inserted butterfly needle on the opposite arm or from a peripheral site if the patient has a central venous catheter immediately prior to the 765IGF-MTX infusion, 5 min before the infusion ends, and at the following time points after completion of the infusion: 30 min, 60 min, 2 h, 4 h, 6 h, 8 h, and 24 h, (windows as above [Research-Related Procedures table, footnote 1]). The 10 h time point will be collected on day 1 but not day 15. IGF-MTX and MTX unbound to IGF toxicokinetic analysis will be performed. These time points are based on pharmacokinetics in dogs. Please see the laboratory manual for PK sample collection procedures.

9.1.2. Pharmacokinetic Sample Processing

Blood samples (6 mL) will be collected in 6-mL EDTA (purple top) tubes. The tube should be gently inverted a few times for complete mixing with the anticoagulant. The exact time of sample collection should be recorded on the tube label and Pharmacokinetics Data Form provided. The tube should be kept on wet ice until centrifugation. Within 120 minutes of blood collection, centrifuge each blood sample at approximately 3,000 X g for 5-10 minutes at 4°C. Aliquots, approximately 0.5 mL each, will be pipetted into 4 separate plastic centrifuge tubes and frozen at -80°C until analysis. Please see the laboratory manual for PK sample collection procedures.

765IGF-MTX, 765IGF, methotrexate and 7-OH-methotrexate plasma concentrations will be determined using validated assays under GLP conditions at the Toxicology Research Laboratory, University of Illinois at Chicago.

9.1.3. Pharmacokinetic Parameter Determination

The pharmacokinetics of the 765IGF-Methotrexate, 765IGF, methotrexate and 7-OH methotrexate will be analyzed by compartmental and noncompartment approaches. Non-compartmental analysis of the plasma concentration-time data for each of the compounds of interest will be performed using WinNonlin 6.3 (Pharsight, St Louis, MO). Pharmacokinetic parameters to be estimated include: 1). area under the drug plasma concentration-time curve from the start of the infusion to the time of the last quantifiable plasma concentration (AUC_{0-t}), 2) AUC from the start of the infusion to infinity ($AUC_{0-\infty}$), 3). maximum observed plasma concentration (C_{max}), 4). time of maximum plasma concentration (T_{max}) and 5). terminal elimination constant (λ_z).

Plasma concentration versus time data for the compounds of interest will be fit individually and simultaneously to appropriate models using nonlinear mixed effects modeling as implemented in NONMEM (version7.3). Data will be modeled with individual and population approaches. One, two, and three-compartment models incorporating parent and metabolite disposition will be evaluated. First order conditional estimation,

Monte Carlo expectation maximization and Monte Carlo Bayesian methods will be explored for estimating the maximum likelihood.

If anti-765IGF antibodies are detected in some or all patients, the effect of the presence of these antibodies on the pharmacokinetic parameters will be investigated. This will be done, for instance, by comparing pharmacokinetic parameters in the first dose, when no anti-drug antibodies could be present, with the parameters in later doses after anti-765IGF antibodies have been shown to have developed, and by comparing the parameters in patients who have anti-765IGF antibodies with those that do not.

